APPENDIX B: LAB PROCESSING FLOW SHEET: CLINICAL/ SAFETY LAB TESTS

Protocol # 15-0015

Instructions- All specimens must be recorded on a form similar to the one below including the visit time/study ID number, tube type, specimen test, processing and storage instructions

Visit/Time of Draw	Tube Type/Quantity	Test/Assay/Derivative	Processing/Aliquot/Storage/Shipping
Screening Day -4 to -1, Visit 00A	Stool collection vial for Stool Evaluation	Rapid Stool EIA for Giardia or E. histolytica EIA stool antigen test if positive Wet mount Concentration and Trichrome staining Qualitative PCR for Giardia and Entamoeba	Stools kept cold and shipped daily to icddr,b or Rajshahi hospital- See Lab SOPs
Screening Day -4 to -1, Visit 00B	Urine collection vial	Dip stick for protein Pregnancy testing	Performed in icddr,b or Rajshahi Hospital or designated lab,
	Purple top tube (7mls)	Complete blood count	Kept at room temp and transferred same day to lab for analysis
	Serum separator tube (10 ml)	BUN, creatinine, SGOT, SGPT	Kept at room temp and transferred same day to lab for analysis Left over serum aliquoted and kept at -80°C
Enrollment Day 1, Visit 01	Stool collection vial for Full Stool Evaluation (+ 1 Day)	Antigen testing for Giardia or E. histolytica Wet mount Concentration and Trichrome staining Qualitative PCR for Giardia and Entamoeba Quantitative PCR for Giardia or Entamoeba in positive stools	Specimens processed as above Processed as above Fixed stool stored at room temp Processed as above Extracted DNA from stool obtained before first auranofin dose. Shipped every 1-3months to UCSD for quantitative PCR
Day 3, Visit 03	Stool collection vial for Full Stool Evaluation (+1 day)	Refer to Day 1 (Not performed on patients who receive metronidazole prior to completing dosing regimen)	Refer to Day 1
Day 5, Visit 05	Stool collection vial for Full Stool Evaluation (+ 1 day)	Refer to Day 1 (Not performed on patients who receive metronidazole prior	Refer to Day 1

		to completing dosing regimen)	
Day 7, Visit 07	Stool collection vial for Full Stool Evaluation (+1 Day)	Refer to Day 1 (Not performed on patients who receive metronidazole prior to completing dosing regimen)	Refer to Day 1
	Urine Collection Vial	Urine Dip stick for protein	Refer to Screening Visit 00B
	Purple top tube (7mls)	Complete blood count and differential	Refer to Screening Visit 00B
	SST (10 ml)	BUN, Cr, SGOT, SGPT,	Refer to Screening Visit 00B
Day 14, Visit 08 +/- 3 days	Stool collection vial for Full Stool Evaluation	Refer to Day 1 If positive at Day 14, perform parasite genotyping. (Not performed on patients who receive metronidazole prior to completing dosing regimen)	Refer to Day 1 Stored DNA sent to UVA for parasite genotyping every 1-3 months
Day 28, Visit 09 +/- 3 days	Stool collection vial for Full Stool Evaluation	Refer to Day 1 If positive at Day 14, perform parasite genotyping. (Not performed on patients who receive metronidazole prior to completing dosing regimen)	Refer to Day 1 Stored DNA sent to UVA for parasite genotyping every 1-3 months

**APPENDIX C: ICDDR,B NORMAL LABORATORY VALUES
(APPLICABLE FOR BOTH SITES)**

	Male	Female
White Blood cells ($10^9/L$)	4.0 – 11.0	same
Platelets ($10^9/L$)	150.0 – 450.0	same
Hemoglobin (gm/dL)	12.5 – 17.5	11.5 – 16.5
Blood urea nitrogen (mg/dL)	5 – 24	same
Creatinine (umol/L)	53-106	44-97
AST/SGOT (U/L)	0.01 – 38.0	0.01 – 32.0
ALT/SGPT (U/L)	0.01 – 41.0	0.01 – 31.0

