3 OBJECTIVES

3.1 Study Objectives

Auranofin is a “repurposed” drug with established pharmacology and is approved for human use by the FDA. We will assess clinical efficacy for two new indications, amebiasis and giardiasis, with a randomized Phase IIa, placebo-controlled, single-blinded, superiority trial comparing auranofin for treatment of amebiasis and giardiasis to placebo in adults. Resolution of diarrhea and clearance of parasites will be the endpoints, and all subjects who remain positive at Day 28 for giardiasis or amebiasis will receive standard of care treatment with metronidazole. Ultimately, the goal will be to expand the trial to include symptomatic children after proving efficacy and safety in adults.

All subjects will have the same screening protocol, but the trial will evaluate subjects with amebiasis or giardiasis with separate primary and secondary endpoints.

Asymptomatic subjects enrolled under prior versions of the protocol will be analyzed as per the corresponding objectives and study SAP.

Primary *E. histolytica*:

To compare the proportion of subjects with stools positive by rapid EIA and positive antigen detection EIA for *E. histolytica* at enrollment with resolution of diarrhea (less than 3 loose stools/24 hours) by Day 7.

Secondary *E. histolytica*:

- To compare the proportion of subjects with positive rapid EIA and positive antigen detection EIA for *E. histolytica* and trophozoites on smear (wet mount or concentrated trichrome) at enrollment with parasitological response (no detection of trophozoites on microscopic exam by Day 7).
- To compare the proportion of subjects with positive rapid EIA and positive antigen detection EIA for *E. histolytica* and trophozoites on smear at enrollment with parasitological response (no detection of trophozoites on microscopic exam) by Day 3 and 5.
- To compare the rate of decrease in trophozoite/cyst load by qPCR in stools by Days 3, 5, and 7.
- To compare the proportion of subjects with negative stool antigen test by Days 3, 5, 7, and 14.

- To compare the proportion of subjects with sustained cure (no detection of trophozoites by microscopic exam) at 14 and 28 days.
- To compare the proportion of subjects with relapse (same strain) or re-infection (new strain) with positive stools at 14 and/or 28 days by genotyping the initial vs. subsequent strain.
- To compare the time to resolution of diarrhea (less than 3 loose stools/24 hours)

Primary *Giardia*:

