3.2.2 Secondary Outcome Measures

1. *E. histolytica*:

- a. Proportion of subjects with positive rapid EIA and positive antigen detection EIA for *E. histolytica* and trophozoites on smear at enrollment with parasitological response (no detection of trophozoites on microscopic exam) by Day 7.
- b. Proportion of subjects with positive rapid EIA and positive antigen detection EIA for *E. histolytica* and trophozoites on smear at enrollment with parasitological response (no detection of trophozoites on microscopic exam) by Day 3 and 5.
- c. Rate of decrease of trophozoite/cyst load by qPCR in stools by Days 3, 5, and 7
- d. Proportion of subjects with negative stool antigen test by Days 3, 5, 7, and 14
- e. Proportion of subjects with sustained cure (no detection of trophozoites by microscopic exam) at 14 and 28 days
- f. Proportion of subjects with relapse (same strain) or re-infection (new strain) with positive stools at 14 and 28 days by genotyping the initial vs. subsequent strain
- g. Time to resolution of diarrhea (less than 3 loose stools/24 hours)

2. *Giardia*:

- a. Proportion of subjects with positive rapid EIA and positive antigen detection EIA for *Giardia* and trophozoites on smear at enrollment with parasitological response (no detection of trophozoites on microscopic exam) by Day 3 and 5
- b. Rate of decrease of trophozoite/cyst load by qPCR in stools by Days 3 and 5
- c. Proportion of subjects with negative stool antigens by days 3 and 5.
- d. Proportion of subjects with sustained cure (no detection of trophozoites by microscopic exam) at 14 and 28 days
- e. Proportion of subjects with relapse (same strain) or re-infection (new strain) with positive stools at 14 and 28 days by genotyping the initial vs. subsequent strain
- f. Time to resolution of diarrhea (less than 3 loose stools/24 hours)

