a. *Pregnancy testing at both hospital sites.* Upon screening: as a condition of enrollment, all women of child bearing age must agree to have a pregnancy test, receive the results, and use effective birth control for the next four months. Testing will be performed on urine using HCG test strip assays. If the test is positive or the woman is breastfeeding, they will not be enrolled, as auranofin is contraindicated in pregnant or breastfeeding women. Women who are enrolled in the study will continue their current effective birth control for 4 months after enrollment.

b. *Urine for proteinuria.* On Visit 00B and 7: urine will be collected from all participants for proteinuria assessment via dipstick testing. Proteinuria testing will be performed at the icddr,b

3. Blood testing: Blood will be drawn for a complete blood count, BUN, creatinine, ALT, and AST on Visit 00B and Day 7. Blood tests will be collected at the icddr,b Hospital or Rajshahi Hospital or Clinic and transported to the respective clinical laboratory.

4. *E. histolytica* and *Giardia* genotyping: Any stool specimen that is still positive for *Entamoeba* or *Giardia* cysts or trophozoites at Days 14 and 28 will have DNA genotyping of the parasite performed on de-identified specimens of extracted DNA. The genotypes from initial and final isolates will be compared to allow determination of the rate of relapse or re-infection without linking to individual patients. The genotyping will be performed off-site at the University of Virginia. There will be no human DNA genotyping performed.

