Sustained cure on Day 28 is defined for the asymptomatic amebiasis group to be no detection of cysts or trophozoites on microscopic exam or negative antigen detection on Days 7, 14, and 28 (if specimens are obtained at each time point). ***Sustained cure on Day 28*** is defined for the symptomatic amebiasis group to be no detection of trophozoites on microscopic exam on Days 7, 14, and 28 (if specimens are obtained at each time point). It is defined analogously for the giardiasis groups but is based on measurements taken on Day 5, 14, and 28.

Relapse at Day X is defined as having a positive stool PCR at day X that is identified via genotyping to be identical to the strain of the original infection.

Reinfection at Day X is defined as having a positive stool PCR at day X that is identified via genotyping to be non-identical to the strain of the original infection.

In the two above definitions, the ***original infection*** is defined to be the strain of parasite measured in the stool sample collected on Visit 01.

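### Appendix B makes Day 28 genotyping depend on a positive Day 14 stool, contradicting Protocol Section 8.2.1 and the SAP definitions of relapse and reinfection

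*Protocol*

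**What the plan says.** Protocol Appendix B lists, visit by visit, the specimen, the tests and the handling. Its Day 14 (Visit 08) row gives the genotyping condition as "If positive at Day 14, perform parasite genotyping". The Day 28 (Visit 09) row gives the same condition, still naming Day 14.

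The other texts that set or use the genotyping trigger are these:

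- Protocol Section 8.2.1 item 4 covers stools in which the parasite is still found as "cysts or trophozoites at Days 14 and 28 will have DNA genotyping of the parasite performed on de-identified specimens of extracted DNA". Its stated purpose is: "The genotypes from initial and final isolates will be compared to allow determination of the rate of relapse or re-infection".
- Protocol Section 3.1 frames the objective, for each infection, as relapse or re-infection "with positive stools at 14 and/or 28 days by genotyping the initial vs. subsequent strain".
- Protocol Section 3.2.2 lists the secondary outcome for each infection: "Proportion of subjects with relapse (same strain) or re-infection (new strain) with positive stools at 14 and 28 days by genotyping".
- SAP Section 3.3 works one day at a time: "Relapse at Day X is defined as having a positive stool PCR at day X that is identified via genotyping" as the Visit 01 strain. The companion definition is: "Reinfection at Day X is defined as having a positive stool PCR at day X that is identified via genotyping to be non-identical" to that strain.
- SAP Section 8.2.1 plans Day 28 summaries of relapse and reinfection in Table 33 (amebiasis) and Table 34 (giardiasis), to be repeated for the symptomatic population.

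**The concern.** The Day 28 row tells the laboratory to decide on Day 28 genotyping from the Day 14 result. No other passage does this. A parasite found at Day 28 in a subject who was negative at Day 14 needs a genotype before it can be called the same strain or a new one, and the row would not produce it.

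A gap created this way would not be random, because it is defined by the Day 14 result. If the arms differ in how many subjects are negative at Day 14, they also differ in how many can fall into the gap. Should auranofin clear more infections by then, more auranofin subjects would be exposed to it, and counting ungenotyped subjects as free of relapse would favor auranofin.

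The planned handling of missing data would help little. SAP Section 6.5 applies multiple imputation to the binary secondary outcomes. Under the literal row, no Day 14-negative subject would have an observed Day 28 relapse or reinfection. Any imputed split for them would have to be borrowed from subjects who were positive at Day 14.

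**Working it through.** The plan states no figure on this point, and no sample size or power calculation depends on it. The check sets the two rules side by side for each possible pair of Day 14 and Day 28 results.

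| Day 14 | Day 28 | Section 8.2.1 and SAP 3.3 | Appendix B Day 28 row, read literally |
|---|---|---|---|
| positive | positive | Day 28 stool genotyped | Day 28 stool genotyped |
| positive | negative | Day 14 stool genotyped; nothing to type at Day 28 | Day 14 stool genotyped; Day 28 typing also called for, on a negative stool |
| negative | negative | none | none |
| negative | positive | Day 28 stool genotyped | **not genotyped** |
| no stool | positive | Day 28 stool genotyped | **not genotyped** |

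1. The required genotype is missing only in the last two lines.
2. The second line shows that the literal row also asks for something that cannot be done, namely typing a parasite in a negative stool. Together with the identical wording in the row above, this suggests carried-over text rather than an intended rule, although the documents do not say so.
3. A subject who clears by Day 5 or Day 7 and is positive again at Day 14 is genotyped under both rules.
4. The SAP definitions do not require clearance before Day X. A persistent positive of the original strain therefore counts as relapse, and it is genotyped under both rules.
5. Tables 33 and 34 have three columns: relapse, reinfection, and either. The first two cannot be filled for the last two patterns. The third could arguably be filled from PCR alone, since a strain is either identical to the Visit 01 strain or not.

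Size: the documents give no frequency for the affected patterns. Let p be the assumed proportion of an arm of 34 (Protocol Section 11.2) that falls into them. The expected number per arm is 34 × p:

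- p = 5%: 34 × 0.05 = 1.7
- p = 10%: 34 × 0.10 = 3.4
- p = 20%: 34 × 0.20 = 6.8

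That is about 2 to 7 subjects per arm over the assumed range.

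A second mismatch shows up in the same comparison. Section 8.2.1 item 4 takes positive to mean cysts or trophozoites, SAP Section 3.3 takes it to mean stool PCR, and the genotyping line of Appendix B does not say. A Day 28 stool that is positive by PCR but shows no parasite on microscopy would enter the SAP outcome without being selected for genotyping under Section 8.2.1. The word still in Section 8.2.1 could also be read as requiring persistence from an earlier visit.

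**The case against.** The strongest reply is that one cell in an appendix is being read against the rest of the protocol. Appendix B introduces itself as a model for a recording form, refers to laboratory SOPs, and Section 8.2.3 leaves further specimen instructions to the Manual of Procedures. None of those is available here. Genotyping is done off-site, at the University of Virginia. The objectives, the outcome measures, Section 8.2.1 and the SAP all point to typing Day 28 positives in their own right, so staff may well do so.

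Part of this stands. The documents do not show which text governs in practice, so the loss is conditional on the laboratory working from Appendix B. But the row does state when a test is to be done, and no text ranks Section 8.2.1 above it. The clause in Protocol Section 11.4 that gives the SAP precedence covers only that section.

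A reader might infer more than the documents support:

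- *That every subject who clears and then recurs goes untyped.* Only those first positive again after Day 14, or with no Day 14 stool, are affected.
- *That these are the cases the outcome is about.* The SAP definitions count persistent positives as well, and no text says that a single negative Day 14 stool proves clearance.
- *That the data are lost for good.* Section 8.2.1 has DNA obtained from Day 28 stools, and Section 14.7 keeps samples that test positive in the freezer for the duration of the study. Missed genotyping is therefore probably recoverable.

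**Conclusion.** The Day 28 row of Appendix B is wrong as written and contradicts Protocol Section 8.2.1 item 4, the objectives in Section 3.1 and SAP Section 3.3. If it is followed literally, subjects who are negative or gave no stool at Day 14 and are positive at Day 28 cannot be assigned to relapse or reinfection in the Day 28 outcome. On an assumed frequency of 5% to 20%, that is about 2 to 7 of 34 subjects per arm. The frequency is an assumption, and no document reports that any specimen was in fact skipped.

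The reach is one secondary outcome in each disease group. The primary endpoints, alpha and power are unaffected. This is an inconsistency that should be corrected, not a flaw in the design.

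**What to change.** 1. In the Day 28 (Visit 09) row of Appendix B, replace Day 14 with Day 28, so that genotyping depends on the Day 28 stool.
2. State one definition of a positive stool and use it in Appendix B, Section 8.2.1 item 4 and SAP Section 3.3. In the same edit, make clear in Section 8.2.1 that a positive at Day 28 qualifies whatever the Day 14 result.
3. Check the laboratory records for Day 28 positives that were not genotyped and, if there are any, genotype them from stored DNA against the Visit 01 strain.

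The first change is one number in one row. The second is a short wording change in each document. The third costs a record check plus genotyping that Section 8.2.1 already plans for microscopy-positive stools. It would add tests only if the agreed definition also takes in stools positive by PCR alone.

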BUN	Blood Urea Nitrogen
C	Celsius
CI	Confidence Interval
CRF	Case Report Form
DMID	Division of Microbiology and Infectious Diseases
DSMB	Data and Safety Monitoring Board
EDC	Electronic Data Capture
ELISA	Enzyme-linked Immunosorbent Assay
ER	Emergency Room
F	Fahrenheit
GGT	Gamma Glutamyl Transferase
GMT	Geometric Mean Titer
GMFR	Geometric Mean Fold Rise
icddr,b	International Center for Diarrheal Disease Research, Bangladesh
ICH	International Conference on Harmonisation
IRB	Institutional Review Board
ITT	Intention to Treat
L	Liter
LLN	Lower Limit of Normal
mcg	Microgram
MedDRA	Medical Dictionary for Regulatory Activities
mEq	Milliequivalent
mg	Milligram
mITT	Modified Intention to Treat
mL	Milliliter
MAR	Missing at Random

List of Abbreviations (continued)

MCAR	Missing Completely at Random
MNAR	Missing Not at Random
N	Number (typically refers to subjects)
NIH	National Institutes of Health
PI	Principal Investigator
PP	Per Protocol
PT	Preferred Term
RBC	Red Blood Cell
RCD	Reverse Cumulative Distribution
SAE	Serious Adverse Event
SD	Standard Deviation
SDCC	Statistical and Data Coordinating Center
SMC	Safety Monitoring Committee
SOC	System Organ Class
SOP	Standard Operating Procedures
U	Units
ULN	Upper Limit of Normal
WBC	White Blood Cell
WHO	World Health Organization

1. PREFACE

The Statistical Analysis Plan (SAP) for “Phase IIa Randomized, Single-blinded, Placebo-controlled Clinical Trial of the Reprofiled Drug Auranofin for GI Protozoa” (DMID Protocol 15-0015) describes and expands upon the statistical information presented in the protocol.

This document describes all planned analyses and provides reasons and justifications for these analyses. It also includes sample tables, listings, and figures planned for the final analyses. Regarding the final analyses and Clinical Study Report (CSR), this SAP follows the International Conference on Harmonisation of Technical Requirements for Registration of Pharmaceuticals for Human Use (ICH) Guidelines, as indicated in Topic E3 (Structure and Content of Clinical Study Reports), and more generally is consistent with Topic E8 (General Considerations for Clinical Trials) and Topic E9 (Statistical Principles for Clinical Trials). The structure and content of the SAP provides sufficient detail to meet the requirements identified by the FDA and ICH, while all work planned and reported for this SAP will follow internationally accepted guidelines published by the American Statistical Association and the Royal Statistical Society for statistical practice.

This document contains four sections: (1) a review of the study design, (2) general statistical considerations, (3) comprehensive statistical analysis methods for efficacy and safety outcomes, and (4) a list of proposed tables and figures. Within the table, figure, and listing mock-ups (Appendices 1, 2, and 3), references to CSR sections are included. Any deviation from this SAP will be described and justified in protocol amendments and/or in the CSR, as appropriate. The reader of this SAP is encouraged to also review the study protocol for details on conduct of the study and the operational aspects of clinical assessments.

2. INTRODUCTION

This study investigates the effectiveness of auranofin for two gastrointestinal protozoa: *E. histolytica* and *Giardia*. This proposed clinical trial follows from key findings in studies supported by U01 AI0778822 entitled, “Novel Therapeutics for Class B Protozoa,” to design and develop highly effective antiparasitic agents for Class B Protozoa. The development of the first high-throughput whole cell screens for *E. histolytica* (Debnath, 2012) and *G. lamblia* (Gut et al., 2011) against FDA-approved drugs and bioactive compounds (a “repurposing” screen), found that auranofin had a ten-fold lower IC₅₀ (0.5 μ M) compared with metronidazole (5.2 μ M) for *E. histolytica* and an equivalent IC₅₀ for *Giardia* (4.0 μ M). Auranofin is an orally available gold-containing compound that has been in clinical use in the treatment of rheumatoid arthritis for 25 years. As previous research has found auranofin to be the first drug active against *Entamoeba* and *Giardia* with a clearly defined target, the FDA has given auranofin Orphan Drug status.

This study is a Phase IIa clinical trial conducted in Bangladesh. The initial plan for this study included a single site, the International Center for Diarrheal Disease Research, Bangladesh (icddr,b). The study initially planned to enroll 136 males and non-pregnant females aged 18 to 65 years with asymptomatic amebiasis (68 subjects) or giardiasis (68 subjects). Participants within each disease group were to be randomized in a 1:1 ratio to receive auranofin or a placebo. The amebiasis group was to receive 6 mg auranofin (or placebo) daily for seven days while the giardiasis group was to receive 6 mg auranofin (or placebo) daily for five days. The initial primary goal of the study, reflected in versions 1 - 4 of the protocol, was to compare the proportion of subjects with parasitological response, defined as no detection of cysts or trophozoites on microscopic exam or negative antigen detection, between treatment arms by Day 7 for amebiasis and by Day 5 for giardiasis.

However, the protocol endpoints and study population were revised because after screening 2,396 people during 17 months with only 34 enrolling into the study, it became apparent that enrolling 136 asymptomatic subjects would be infeasible. For this reason, eligibility criteria were revised, starting with protocol version 5, to enroll symptomatic rather than asymptomatic adult patients (still with amebiasis or giardiasis). The goal, as before, was to enroll 68 in each disease group and randomize in a 1:1 ratio within each disease group to receive either auranofin or placebo. The dosing regimen was unchanged, but the primary outcome was revised for the new (symptomatic) study population. The new primary outcome is resolution of diarrhea (less than 3 loose stools / 24 hours) by Day 7 for the symptomatic amebiasis group and by Day 5 for the symptomatic giardiasis group. Furthermore, in version 7 of the protocol, a new site was also added (Rajshahi Medical College Hospital), after which randomization was stratified by site as well as disease group. The protocol revision specified that the asymptomatic and symptomatic subjects would be analyzed separately.

The study populations, study design, and primary outcome for each of these populations are summarized by protocol version in [Table 1](#):

Table 1: Summary of Study Population, Study Design, and Primary Outcome by Protocol Version

Protocol Versions	Study Population	Target Sample Size	Treatment Allocation	Dosing Regimen	Primary Outcome
1-4	Asymptomatic amebiasis	68	1:1 (auranofin: placebo)	7 days	Parasitological response (no detection of cysts or trophozoites on microscopic exam or negative antigen detection) by Day 7
	Asymptomatic giardiasis	68	1:1 (auranofin: placebo)	5 days	Parasitological response (no detection of cysts or trophozoites on microscopic exam or negative antigen detection) by Day 5
5-7	Symptomatic amebiasis	68	1:1 (auranofin: placebo) ^a	7 days	Resolution of diarrhea (less than 3 loose stools / 24 hours) by Day 7
	Symptomatic giardiasis	68	1:1 (auranofin: placebo) ^a	5 days	Resolution of diarrhea (less than 3 loose stools / 24 hours) by Day 5

^a Randomization was also stratified by site for subjects enrolled under protocol version 7 because a second site was added in that protocol version.

Secondary objectives for the asymptomatic population are summarized in [Table 2](#), while those for the symptomatic population are summarized in [Table 3](#). The changes in secondary outcomes for the symptomatic population are shown in blue in [Table 3](#).

Table 2: Secondary Outcomes for the Asymptomatic Study Population

Outcome	Time points, Asymptomatic Amebiasis Group	Time points, Asymptomatic Giardiasis Group
Parasitological response (no detection of cysts or trophozoites on microscopic exam or negative antigen detection)	Days 3 and 5	Day 3
Rate of decrease in trophozoite/cyst load by qPCR in stools	Days 3, 5, and 7	Days 3 and 5
Negative stool antigen test	Days 3, 5, 7, and 14	N/A
Sustained cure (no detection of cysts or trophozoites by microscopic exam or negative antigen detection)	Days 14 and 28	Days 14 and 28
Relapse (same strain) or re-infection (new strain) with positive stools by genotyping the initial vs. subsequent strain.	Day 14 and/or 28	Day 14 and/or 28

Table 3: Secondary Outcomes for the Symptomatic Study Population

Changes to outcomes from the asymptomatic population are shown in blue:

Outcome	Time points, Symptomatic Amebiasis group	Time points, Symptomatic Giardiasis group
Parasitological response (no detection of trophozoites on microscopic exam ^a)	Days 3, 5, and 7 ^b	Day 3 and 5 ^b
Rate of decrease in trophozoite/cyst load by qPCR in stools	Days 3, 5, and 7	Days 3 and 5
Negative stool antigen test	Days 3, 5, 7, and 14	Days 3 and 5
Sustained cure (no detection of trophozoites by microscopic exam) ^c	Days 14 and 28	Days 14 and 28
Relapse (same strain) or re-infection (new strain) with positive stools by genotyping the initial vs. subsequent strain.	Day 14 and/or 28	Day 14 and/or 28
Time to resolution of diarrhea ^d	Assessment over the study period	Assessment over the study period

^a The definition of parasitological response was revised to allow for cysts and remove the antigen test.^b Moved from primary to secondary outcome.^c Modified so definition of “cure” matches the updated definition of parasitological response for this population.^d New outcome for this study population.

